4.0 Test Schedule

NOTE: Variation of ≤ 4 days of scheduled visit is permitted.

Tests and procedures	≤ 21 days prior to registration	≤ 7 days prior to registration	Active Monitoring				
			Prior to dosing on Day 1 of each cycle,* Beginning with Cycle 1 (until PD)	Day 15 of each cycle, Beginning with Cycle 1 (until PD)	Prior to 3 rd and subsequent odd cycles (until PD)	End of Treatment (PD, withdrawal, or removal)	Observation ⁸ : 30 days of End of Treatment
History and exam, wt, ECOG PS	X		X	X		X	X
Height	X						
Adverse event assessment	X		X	X		X	X ⁷
Hematology: CBC/ differential	X		X	X		X	X
Chemistry: SGOT (AST), SGBT (ALT), alk phos, T. bili, creatinine, calcium, phos, glucose, Na, K							
Tumor measurement ¹	X				X	X	
Pregnancy test ²		X	X				
Mandatory archival tissue collection ^{5, R} (See Section 17)	X						
cfDNA ^{4, R}			X		X	X	
ECG ⁶	X		X				
Cancer markers: CEA (colorectal cancer) and CA19-9 (cholangiocarcinoma) ^{4 R}	X				X	X	
Patient Medication Diary ³			X			X	

* Cycle = 28 days.

(Footnotes on next page)

1. Imaging should be done using CT scan (MRI if CT is not feasible). Use same imaging throughout the study. If patient is on study for more than 2 years, allow scans 3-4 months apart.
2. For individuals of childbearing potential only. Negative urine or serum pregnancy test must be done \leq 7 days prior to registration and repeated prior to dosing on day 1 of each cycle. If a patient becomes pregnant during the study the investigator is to stop dosing with study drug(s) immediately. (See Section 10.314 for additional information.)
3. The diary must begin the day the patient starts taking the medication and must be completed per protocol and returned to the treating institution OR compliance must be documented in the medical record by any member of the care team.
4. Mandatory blood draws (STRECK, EDTA and No Additive tubes) for research should not be collected and submitted until after the patient is registered onto the study, and should be done prior to dosing on Cycle 1, Day 1, then Day 1 of subsequent odd cycles, and end of treatment. Kits are required for this collection (See Section 14.0).
5. Receipt of archival tumor tissue is not required for study registration and initiation of therapy. However, it is mandatory to receive the required tissue within 60 days from registration.
6. Dose-escalation phase I, ECG should be done on baseline and Cycle 2, Day 1, measured twice at least 5 minutes apart. For Phase Ib and II – ECG should be done prior to cycle 1 only, then as indicated.
7. Any Adverse event assessment within 30 days of end of treatment will be recorded on the adverse event assessment form in the last cycle of treatment.
8. Treatment decision/patient care for patients who are off protocol treatment is at the discretion of the treating physician. The observation period is recommended by the study protocol but no data collection is required other than adverse event assessment (See Footnote 7)

R Research funded (see Section 19.0)

Event Monitoring: Patients will be followed for survival every 6 months for 3 years from registration. This can be done via a phone call to the patient and does not require the patient to return to the consenting site.

5.0 Grouping Factors:

- Phase I (Dose Escalation)- pancreatic vs.
- Phase I (Dose Escalation)- colorectal vs.
- Phase I (Dose Escalation)- gastroesophageal vs.
- Phase I (Dose Escalation)- biliary tract vs.
- Phase Ib (Dose Expansion)-pancreatic, Unknown/non-HRD patients vs.
- Phase Ib (Dose Expansion)-pancreatic, HRD patients vs.
- Phase II.

6.0 Registration/Randomization Procedures

6.1 Phase I

Prior to discussing protocol entry with the patient, call the ACCRU Registration Office [contact]) for dose level and to ensure that a place on the protocol is open to the patient.

6.11 Registration Procedures

6.111 To register a patient, fax [REDACTED] a completed eligibility checklist to the Academic and Community Cancer Research United (ACCRU) Registration Office between 8 a.m. and 4:30 p.m. central time Monday through Friday.

6.112 Documentation of IRB approval must be on file with ACCRU before an investigator may register any patients. Approvals should be uploaded through the online ACCRU Regulatory Management System (ARMS).

In addition to submitting initial IRB approval documents, ongoing IRB approval documentation must be on file with ACCRU no less than annually. Approvals should be uploaded through the online ACCRU Regulatory Management System (ARMS). If the necessary documentation is not submitted in advance of attempting patient registration, the registration will not be accepted and the patient may not be enrolled in the protocol until the situation is resolved.

Submission of annual IRB approvals to ACCRU is required until the study is closed through your IRB.

6.113 Prior to accepting the registration, registration/randomization application will verify the following:

- IRB approval at the registering institution
- Patient eligibility
- Existence of a signed consent form
- Existence of a signed authorization for use and disclosure of protected health information

6.2 Phase Ib

6.21 Registration Procedures

To register a patient, access the ACCRU web page at [REDACTED] go to the Application section and click on “Registration” and enter the registration/randomization application. The registration/randomization application is available 24 hours a day, 7 days a week. Back up and/or system support contact information is available on the Web site. If unable to access the Web site, call the Academic and Community Cancer Research United (ACCRU) Registration Office at [REDACTED] between the hours of 8 a.m. and 4:30 p.m. Central Time (Monday through Friday).

Instructions for the registration/randomization application are available on the above web page under the Study Resources section, “Application Training.”

Prior to initiation of protocol study intervention, this process must be completed in its entirety and a ACCRU subject ID number must be available as noted in the instructions. It is the responsibility of the individual and institution registering the patient to confirm the process has been successfully completed prior to release of the study agent. Patient registration via the registration/randomization application can be confirmed in any of the following ways:

- Contact the ACCRU Registration Office [REDACTED] If the patient was fully registered, the Registration Office staff can access the information from the centralized database and confirm the registration.
- Refer to “Application Training” at [REDACTED] click on “Registration, Installation & Entry Instructions”.

6.3 Phase II

6.31 Pre-Registration (Step 0)

6.311 To pre-register a patient, access the ACCRU web page at [REDACTED] go to the Application section, click on “Registration” and enter the registration/randomization application. The registration/randomization application is available 24 hours a day, 7 days a week. Back up and/or system support contact information is available on the Web site. If unable to access the Web site, call the Academic and Community Cancer Research United (ACCRU) Registration Office at [REDACTED] between the hours of 8 a.m. and 4:30 p.m. Central Time (Monday through Friday).

Users should refer to the section titled “Pre-Registration Components” for details on how to pre-register a patient to a study. At the time of pre-registration the patient will receive an ACCRU patient identification number. This number is to be used when submitting tissue or blood samples, as applicable for the study (see Section 17.0). Patient pre-registration via the registration/randomization application can be confirmed in any of the following ways:

- Contact the ACCRU Registration Office [REDACTED] If the patient was pre-registered, the ACCRU Registration Office staff can access the information from the centralized database and confirm the registration.
- Refer to “Application Training” at [REDACTED] “Registration, Installation & Entry Instructions”.

6.312 Documentation of IRB approval must be on file with ACCRU before an investigator may pre-register any patients. Approvals should be uploaded through the online ACCRU Regulatory Management System (ARMS).

In addition to submitting initial IRB approval documents, ongoing IRB approval documentation must be on file with ACCRU no less than annually. Approvals should be uploaded online through ARMS. If the necessary documentation is not submitted in advance of attempting patient registration, the registration will not be accepted and the patient may not be enrolled in the protocol until the situation is resolved.

Submission of annual IRB approvals to ACCRU is required until the study has been permanently closed through your IRB.

6.313 Prior to accepting the pre-registration, the registration/randomization application will verify the following:

- IRB approval at the registering institution
- Patient pre-registration eligibility
- Existence of a signed consent form
- Existence of a signed authorization for use and disclosure of protected health information

6.32 Registration (Step 1)

Upon completion of the patient’s submitted blood or tissue evaluation status (see Sections 14.0 and/or 17.0), the person provided on the samples submission form will be contacted by fax with the results of the sample evaluations. If based upon the sample evaluations the subject is approved for registration, the pre-registering institution must register the subject to the protocol.

6.321 To register a patient, access the ACCRU web page at [REDACTED] go to the Application section, click on “Registration” and enter the registration/randomization application. The registration/randomization application is available 24 hours a day, 7 days a week. Back up and/or system support contact information is available on the Web site. If unable to access the Web site, call the Academic and Community Cancer Research United (ACCRU) Registration Office at [REDACTED] between the hours of 8 a.m. and 4:30 p.m. Central Time (Monday through Friday).

Users should refer to the section titled “Pre-Registration Component” for details on how to register a patient on step 2 of a study that has a pre-registration and registration step. The instructions for the

registration/randomization application are available using the Help button. Prior to initiation of protocol treatment, this process must be completed in its entirety and an ACCRU subject ID number must be available as noted in the instructions. It is the responsibility of the individual registering the patient to confirm the process has been successfully completed prior to release of the study agent. Patient registration via the registration/randomization application can be confirmed in any of the following ways:

- Contact the ACCRU Registration Office [REDACTED] the patient was pre-registered, the ACCRU Registration Office staff can access the information from the centralized database and confirm the registration.
- Refer to “Application Training” at [REDACTED] click on “Registration, Installation & Entry Instructions”.

6.322 Documentation of IRB approval must be on file with ACCRU before an investigator may register any patients. Approvals should be uploaded through the online ACCRU Regulatory Management System (ARMS).

In addition to submitting initial IRB approval documents, ongoing IRB approval documentation must be on file with ACCRU no less than annually. Approvals should be uploaded through the online ACCRU Regulatory Management System (ARMS). If the necessary documentation is not submitted in advance of attempting patient registration, the registration will not be accepted and the patient may not be enrolled in the protocol until the situation is resolved.

Submission of annual IRB approvals to ACCRU is required until the study is closed through your IRB.

6.323 Prior to accepting the registration, registration/randomization application will verify the following:

- IRB approval at the registering institution
- Patient eligibility

6.4 Phase I/Ib and II

6.41 Correlative Research

A mandatory correlative research component is part of this study, the patient will be automatically registered onto this component (see Sections 3.0, 14.0 and 17.0).

6.42 At the time of registration, the following will be recorded:

- Patient has/has not given permission to store and use his/her blood sample(s) for future research to learn about, prevent, or treat cancer.
- Patient has/has not given permission to store and use his/her blood sample(s) for future research to learn, prevent, or treat other health problems (for example: diabetes, Alzheimer’s disease, or heart disease).

- Patient has/not given permission to store and use his/her tissue sample(s) for future research to learn about, prevent, or treat cancer.
- Patient has/not given permission to store and use his/her tissue sample(s) for future research to learn, prevent, or treat other health problems (for example: diabetes, Alzheimer's disease, or heart disease).
- Patient has/not given permission for ACCRU to give his/her sample(s) to outside researchers.

6.43 Treatment on this protocol must commence at an ACCRU institution under the supervision of a cancer specialist.

6.44 Treatment cannot begin prior to registration and must begin ≤ 21 days after registration.

6.45 Pretreatment tests/procedures (see Section 4.0) must be completed within the guidelines specified on the test schedule.

6.46 All required baseline symptoms (see Section 10.52) must be documented and graded.

6.47 Study drug is available on site.

6.48 Blood draw kit is available on site.

7.0 Protocol Treatment

7.1 Treatment Schedule – Use actual weight with dose adjustments if weight changes more than 10% from baseline.

Cycle = 28 days

Agent	Route	Day
Nanoliposomal Irinotecan (nal-IRI)	IV	Days 1 and 15
Leucovorin (LV)*	IV	Days 1 and 15, prior to 5-FU
Fluorouracil (5-FU)	IV	Days 1 and 15
Rucaparib	PO	Twice each day on Days 4-13 and Days 18-27 of a 28 day cycle.

*If there is a shortage of leucovorin (LV) in the U.S., and you are unable to obtain access, LV may be held until supply is available. LV will not be administered in the phase Ib/II portion of the study

7.11 Planned Phase I Dose Escalation Levels:

Dose Level	Agent	Dose	Route	Day
DL-2	Nanoliposomal irinotecan (nal-IRI)	43 mg/m2	Intravenous over 90 minutes	Days 1 and 15
	Leucovorin (LV)	400 mg/m2	Intravenous	Days 1 and 15, prior to 5-FU
	Fluorouracil (5-FU)	2000 mg/m2	Intravenous over 46 hours	Days 1 and 15
DL-1	Rucaparib	200 mg	Oral	Twice daily on Days 4-13 and 18-27
	nal-IRI	50 mg/m2	Intravenous over 90 minutes	Days 1 and 15
	LV	400 mg/m2	Intravenous	Days 1 and 15, prior to 5-FU
	5-FU	2400 mg/m2	Intravenous over 46 hours	Days 1 and 15
DL1*	Rucaparib	200 mg	Oral	Twice daily on Days 4-13 and days 18-27
	nal-IRI	50 mg/m2	Intravenous over 90 minutes	Days 1 and 15
	LV	400 mg/m2	Intravenous	Days 1 and 15, prior to 5-FU
	5-FU	2400 mg/m2	Intravenous over 46 hours	Days 1 and 15
DL2-A	Rucaparib	400 mg	Oral	Twice daily on Days 4-13 and days 18-27
	Nanoliposomal irinotecan (nal-IRI)	50 mg/m2	Intravenous over 90 minutes	Days 1 and 15
	Fluorouracil (5-FU)	2400 mg/m2	Intravenous over 46 hours	Days 1 and 15
DL 2-B	Rucaparib	600 mg	Oral	Twice daily on Days 4-13 and days 18-27
	nal-IRI	70 mg/m2	Intravenous over 90 minutes	Days 1 and 15
	LV	400 mg/m2	Intravenous	Days 1 and 15, prior to 5-FU
	5-FU	2400 mg/m2	Intravenous over 46 hours	Days 1 and 15
DL 3	Rucaparib	400 mg	Oral	Twice daily on Days 4-13 and days 18-27
	nal-IRI	70 mg/m2	Intravenous over 90 minutes	Days 1 and 15
	Leucovorin	400 mg/m2	Intravenous	Days 1 and 15, prior to 5-FU
	5-FU	2400 mg/m2	Intravenous over 46 hours	Days 1 and 15
	Rucaparib	600 mg	Oral	Twice each day on

				Days 4-13 and days 18-27
--	--	--	--	--------------------------

* Starting dose level

Only patients with pancreatic, colorectal, gastroesophageal and biliary tract cancers will be included

7.12 Phase Ib Dose Expansion (Phase Ib Study at recommended dose level determined by the Phase I portion):

The recommended dose determined by phase I dose escalation is dose level 2-A (DL2-A in section 7.11)

Agent	Dose	Route	Day
nal-IRI	50 mg/m ² (Recommended Dose Determined by Phase I Dose Escalation)	Intravenous over 90 minutes	Days 1 and 15
5-FU	2400 mg/m ²	Intravenous over 46 hours	Day 1 and 15
Rucaparib	600 mg (Recommended Dose Determined by Phase I Dose Escalation)	Oral	Twice daily on Days 4-13 and days 18-27 (Recommended schedule determined by phase I dose escalation)

7.13 Phase II (Phase II study at recommended dose level determined by the Phase I portion)

Agent	Dose	Route	Day
nal-IRI	Recommended Dose Determined by Phase I Dose Escalation	Intravenous over 90 minutes	Days 1 and 15
5-FU	2400 mg/m ²	Intravenous over 46 hours	Days 1 and 15
Rucaparib	Recommended Dose Determined by Phase I Dose Escalation	Oral	Twice daily on days as determined by Phase I administration schedule

7.14 Pretreatment medication

Agent*	Dose	Route	Day
Dexamethasone	10 mg	IV	Per institutional guidelines
Ondansetron	8mg	IV	Per institutional guidelines

*Other pretreatment meds can be used per institutional guidelines.

7.2 For this protocol, the patient must return to the consenting ACCRU institution for evaluation at least every 14 days during treatment.

7.3 Treatment by a local medical doctor (LMD):

Patients must receive study treatment per protocol at the consenting ACCRU institution. However, patients are allowed to receive supportive care for any adverse events, as needed, at a non-ACCRU institution.

7.4 Phase I/Ib – determination of recommended dose level and dose expansion

7.41 Dose Escalation

7.411 This portion of the study will include patients with metastatic disease from pancreatic cancer (up to 2 lines of prior therapy), colorectal cancer (up to 3 lines of prior therapy), gastroesophageal cancer (up to 1 lines of prior therapy) and biliary tract cancer (BTC; up to 1 line of prior therapy allowed).

7.412 There will be 4 dose levels with two de-escalations to dose level -2 if dose level 1 is deemed intolerable (See Table 1).

7.413 Three patients will be evaluated at each dose level and assessed for dose limiting toxicity (DLT) during cycle 1 (4 weeks). Standard 3+3 dose escalation scheme is utilized (See Section 16.22 for MTD determination). Maximum tolerated dose (MTD) is the highest dose at which no more than 1 of 6 patients will develop a DLT.

7.414 The recommended dose level for Phase 1b and Phase 2 study will be determined based on MTD and discussion between the study team and the sponsor.

7.415 Dose expansion: Following determination of the recommended dose level from the phase I study, the study will proceed to a phase 1b study of patients with metastatic adenocarcinoma of the pancreas who have received no more than 1 line of prior therapy in the metastatic setting. See Schema for further details.

7.416 We will collect plasma samples (for cfDNA) from patients prior to initiation of therapy, prior to 3rd and subsequent odd cycles, and at progression. Paraffin embedded tissue (PET) will be collected as well.

HRD analysis will be performed as a translational component to help correlate with response (prior to therapy) and development of resistance (during and at end of therapy). PET will be used for validation. The test requires ~ 5x 10uM FFPE sections.

7.417 Similar to other follow up studies to NAPOLI, UGT1A1 will not be routinely required or tested. Testing will be performed on individual patients who may experience significant and unexpected toxicities are encountered.

7.418 Investigators are to contact the ACCRU Operations Office via email at [REDACTED] as soon as any dose-limiting toxicity (DLT) occurs.

7.42 Definitions of DLT

Toxicity will be assessed using the NCI CTCAE, version 4.03 unless otherwise specified. A DLT is defined as an AE or abnormal laboratory value (assessed as possibly, probably or definitely related to the study medication) which occurs \leq 28 days following the first dose of MFR (or 1 cycles of therapy, each cycle = 28 days), and meets any of the criteria listed in Table 7.421.

If a patient experiences toxicity that fulfills the criteria for a DLT during the DLT observation window (cycle 1 day 1 through cycle 1 day 28, treatment with the study drug will be interrupted and the toxicity will be followed up. Patients will be allowed to remain on study if the DLT is resolved within 4 weeks at the discretion of the investigator. Patients will continue on study at the next lowest dose level. If treatment is reduced during the DLT observation window or is held for >28 days for any reason, this will be considered a DLT.

7.421 Dose Limiting Toxicities (DLT)

TOXICITY	DLT CRITERIA
Hematology	CTCAE grade 4 neutropenia with fever of any duration, or grade 4 neutropenia lasting more than 5 consecutive days
	CTCAE grade 4 thrombocytopenia lasting more than 5 days, or grade 3 with bleeding
	CTCAE Grade 3 or 4 neutropenia with fever (temperature $\geq 38.5^{\circ}\text{C}$)
Skin and subcutaneous tissue disorders	Rash, hand-foot skin reaction or photosensitivity CTCAE Grade 3 lasting more than 7 consecutive days despite skin toxicity treatment (as per local practice)
Gastro-intestinal	CTCAE grade ≥ 3 nausea or vomiting lasting more than or equal to 48 hrs despite optimal anti-emetic therapy
	CTCAE grade ≥ 3 diarrhea lasting more than or equal to 48 hrs despite optimal anti-diarrhea treatment
Hepatobiliary	CTCAE grade ≥ 3 total bilirubin (excluding any elevations caused by mechanical obstruction of the biliary tree by tumor or stent blockage)
	CTCAE grade ≥ 4 ALT (isolated increases in AST without concomitant increases in ALT will not be considered dose-limiting, because of the non-specific nature of AST)
	Serum alkaline phosphatase CTCAE Grade 4 lasting more than 7 consecutive days
ECG QTc Interval	QTc interval ≥ 501 ms on at least two separate consecutive ECGs taken 5 min apart
Renal	Serum creatinine $> 6x$ ULN
Non-hematologic events	Any non-hematological CTCAE grade ≥ 3 , except for the exclusions noted below
Other	Any related toxicity that delays treatment by > 28 days
Exceptions to DLT criteria	CTCAE grade 3 fatigue lasting fewer than 5 days
	CTCAE grade 3 edema lasting fewer than 5 days
	Grade 3 laboratory abnormalities that are responsive to oral supplementation or deemed by the investigator to be not clinically significant
CTCAE version 4.03 will be used for all grading. Optimal therapy for vomiting or diarrhea will be based in institutional guidelines, with consideration of the prohibited medications listed in this protocol.	

7.5 Phase II - The phase II study in pancreatic cancer will depend on the successful completion of the phase I trial, determination of the recommended dose level and discussion between PI and co-sponsors of the study.

7.51 Following the accrual of the first 6 patients into the phase II portion, we will assess for any unexpected serious toxicities (without halting accrual). If >1 of the first 6 patients experience grade 5 toxicity at least possibly (possible, probable, definite) related to treatment, we will halt accrual and discuss with the sponsors alternative dose levels including the possibility to de-escalate to one dose level. After reinitiating accrual, the patients who were included in the prior dose level cannot be considered for the final analysis and will have to be replaced.

7.52 In the Phase II portion of this study, all patients' tissue samples will be screened for HRD and BRCA-like signature, and only those patients with defects will be selected for the treatment study.

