8.0 Dosage Modification Based on Adverse Events

Strictly follow the modifications in this table for the first **two** cycles, until individual treatment tolerance can be ascertained. Thereafter, these modifications should be regarded as guidelines to produce mild-to-moderate, but not debilitating, side effects. If multiple adverse events are seen, administer dose based on greatest reduction required for any single adverse event observed. Reductions or increases apply to treatment given in the preceding cycle and are based on adverse events observed since the prior dose.

ALERT: *ADR reporting may be required for some adverse events (See Section 10)*

8.1 Dose Modifications for Rucaparib (Based on Adverse Events in Tables 8.2 and 8.3)

Starting Dose Level	1 st Dose Modification	2 nd Dose Modification
600 mg BID	500 mg BID	400 mg BID
400 mg BID	300 mg BID	200 mg BID
300 mg BID	200 mg BID	300 mg QD
200 mg BID	300 mg QD	200 mg QD

NOTE: No more than two dose reductions are allowed.

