8.2 Dose Modifications for Hematologic Toxicities

Worst Toxicity by CTCAE Grade ^{b, c}	nal-IRI or 5-FU ^e
Grade 2 neutropenia (ANC < 1500 – 1000 cells/mm ³)	100% of previous dose
Grade 3 or 4 neutropenia (ANC ≤ 1000 cells/mm ³) or febrile neutropenia ^a	^{1st} occurrence: Delay treatment ^d until resolved to ≤ Grade 2, then reduce dose to by 25% ^{2nd} occurrence: Delay treatment ^d until resolved to ≤ Grade 2, then reduce dose another 25% (50% of original dose)
≤Grade 2 thrombocytopenia (Grade 2: platelets ≤75,000/mm ³ -50,000/mm ³)	If Grade 2: 100% of previous dose
Grade 3-4 thrombocytopenia: platelets <50,000/mm ³)	If Grade ≥3: ^{1st} occurrence: Delay treatment ^d until resolved to ≤ Grade 2, then reduce dose by 25% ^{2nd} occurrence: Delay treatment ^d until resolved to ≤ Grade 2, then reduce dose another 25% (50% of original dose)

^aConsider the use of G-CSF for patients who experience ≥ Grade 3 neutropenia or febrile neutropenia.

^bAnemia: no changes; transfuse as needed.

^cLymphocytopenia: no changes.

^dFor Grade 3 and worse neutropenia and/or platelets, delay all agents (5FU, leucovorin, nal-IRI and rucaparib) until resolve to ≤ Grade 2.

^eThe dose of the agent (5FU or nal-IRI) that is most likely the cause of the hematologic toxicity, as per investigator's assessment, will be reduced when resuming treatment.

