Grade ≥ 4	
 • Hold rucaparib • Monitor liver function tests weekly until resolution to \leq Grade 2 		Resume with a dose reduction and monitor liver function tests weekly for 3 weeks after restarting.

a. NCI-CTCAE = National Cancer Institute - Common Terminology Criteria for Adverse Events, version 4.03

b. Treatment with rucaparib should be held until the toxicity resolves to \leq CTCAE Grade 2. Twice daily dosing may then be resumed at either the same dose or a lower dose, per investigator discretion. If treatment is resumed at the same dose, and the patient experiences the same toxicity, the dose should be reduced following resolution of the event to \leq CTCAE Grade 2. If the patient continues to experience toxicity, additional dose reduction steps are permitted; however, the investigator should contact ACCRU (see Protocol Resource page) before reducing to 300 mg BID. If a patient continues to experience toxicity despite dose reduction steps to 300 mg BID, or if dosing with rucaparib is interrupted for $>$ 14 consecutive days due to toxicity, treatment should be discontinued, unless otherwise agreed between the investigator and ACCRU.

8.3 Dose Modifications for Non-Hematologic Toxicities Other than grade 3 ALT/AST (follow recommendation by Table 8.22), Fatigue and Grade 3 Anorexia^{a, d}

Worst Toxicity by CTCAE Grade*	na1-IRI	5-FU
Grade 1 diarrhea ^b	Continue same dose	Continue same dose
Grade 1 or 2 including diarrhea (except alopecia, nausea and vomiting)	Withhold na1-IRI then resume once resolved to grade 1 at 100% of previous dose	Withhold 5-FU, then resume once resolved to grade 1 at 100% of previous dose, except for Grade 2 hand foot syndrome, Grade 2 cardiac toxicity, or any grade neurocerebellar toxicity
Grade 3 or 4, including diarrhea ^c (except alopecia, nausea and vomiting)	Withhold na1-IRI then resume once resolved to grade 1 per below: 1 st occurrence: Reduce dose to by 25% 2 nd occurrence: Reduce dose another 25% (50% of original dose)	Withhold 5-FU then resume once resolved to grade 1 per below: 1 st occurrence: Reduce dose by 25% 2 nd occurrence: Reduce dose another 25% (50% of original dose) *except for Grade 3 or 4 hand foot syndrome

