Grade 3 or 4 nausea and/or vomiting, despite anti-emetic therapy	Optimize anti-emetic therapy AND reduce dose to 50 mg/m ² , if starting dose is 70 mg/m ² .. If the patient is already receiving 50 mg/m ² , reduce dose to 43 mg/m ² , ^c	Optimize anti-emetic therapy AND reduce dose by 25%; if the patient is already receiving a reduced dose, reduce dose an additional 25% ^e
Grade 2 hand foot syndrome	100% of previous dose	1 st occurrence: Reduce dose by 25% 2 nd occurrence: Reduce dose another 25% (50% of original dose) ^d
Grade 3 or 4 hand foot syndrome	1 st occurrence: Reduce dose to 50 mg/m ² , if starting dose is 70 mg/m ² . 2 nd occurrence: Reduce dose to 43 mg/m ²	Discontinue therapy
Any grade neurocerebellar or ≥ Grade 2 cardiac toxicity	No dose modifications required ^d	Discontinue therapy
Sensory neuropathy	No dose modifications required ^d	No dose modifications required ^d

* Located at [REDACTED]

^a Fatigue and Grade 3 anorexia do not require dose modification.

^b Grade 1 diarrhea: 2-3 stools/day > pretreatment.

^c Grade 2 diarrhea: 4-6 stools/day > pretreatment; Grade 3 diarrhea: 7-9 stools/day > pretreatment; Grade 4 diarrhea: > 10 stools/day > pretreatment.

^d Any toxicity ≥ Grade 2, except anemia and alopecia, can justify a dose reduction if medically indicated.

^e Patients who require more than 2 dose reductions must be withdrawn from the study.

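### If the dose level in 7.42 is a 7.11 level, 7.42 and Section 8 give a DL2-A patient resuming after a cycle-1 DLT different chemotherapy doses, and no rule says which governs

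*Combined protocol and SAP*

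**What the plan says.** **Section 7.42.** After a DLT, treatment is interrupted. If the event resolves within four weeks the patient may stay on study at the investigator's discretion, and then: "Patients will continue on study at the next lowest dose level". The DLT window is cycle 1, days 1 to 28.

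**Section 8.0.** "Strictly follow the modifications in this table for the first" two cycles; after that the modifications become guidelines.

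**Same events under both rules.** Table 7.421 counts as DLTs prolonged or febrile grade 4 neutropenia, prolonged grade 4 thrombocytopenia, grade 3 or higher nausea, vomiting or diarrhoea persisting 48 hours despite treatment, and "Rash, hand-foot skin reaction or photosensitivity CTCAE Grade 3 lasting more than 7 consecutive days". Section 8 prescribes doses for these too:

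- Table 8.2, grade 3-4 neutropenia or thrombocytopenia: a 25% cut, applied to whichever of 5-FU or nal-IRI is "most likely the cause of the hematologic toxicity".
- Table 8.3, grade 3-4 events including diarrhoea: "Withhold 5-FU then resume once resolved to grade 1 per below", with a 25% cut at first occurrence. The nal-IRI cell is parallel.
- Table 8.3, grade 3-4 nausea or vomiting: for 5-FU, "Optimize anti-emetic therapy AND reduce dose by 25" per cent; for nal-IRI, 50 goes to 43 mg/m2.
- Table 8.3, grade 3-4 hand-foot syndrome: 5-FU is discontinued.

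**Rucaparib.** Section 8.1 is headed "Dose Modifications for Rucaparib (Based on Adverse Events in Tables 8.2 and 8.3" and steps 600 mg BID to 500 mg BID. Section 8.21 asks for a one-level reduction after grade 3 or higher non-haematologic toxicity, without naming the agent.

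**The concern.** A patient who resumes after a resolved cycle-1 DLT would ordinarily still be inside the two cycles in which Section 8 is mandatory, so both rules apply at once. On the 7.11 reading they cannot both be followed literally. 7.42 leaves nal-IRI and 5-FU at full dose and takes the whole reduction from rucaparib. Section 8 reduces or stops the cytotoxic agents.

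The stakes are patient safety and consistency between sites. Taken literally, 7.42 would restart full-dose 5-FU after a hand-foot DLT for which Table 8.3 stops it. It would also add leucovorin, which 15.493 warns may increase 5-FU toxicity. Two sites could handle the same DLT differently, each with a section of the protocol to cite.

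**Working it through.** The protocol gives no figure of its own here, so the check sets the two rules side by side.

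**Inputs.** DL2-A is nal-IRI 50 mg/m2, 5-FU 2400 mg/m2 and rucaparib 600 mg BID, without leucovorin (7.11, confirmed by 7.12). Section 16.228 places DL2-A between DL1 and DL2-B, so the level below it is DL1: 50 / 2400 / rucaparib 400 mg BID plus leucovorin 400 mg/m2. The row labels of the 7.11 table are displaced in the extracted text, so DL1 is read from the blocks of agents.

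**Under 7.42 (move to DL1).** nal-IRI 50/50 - 1 = 0%; 5-FU 2400/2400 - 1 = 0%; rucaparib 400/600 - 1 = -33%; leucovorin goes from none to 400 mg/m2.

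**Under Section 8 (first occurrence, from DL2-A).** 50 x 0.75 = 37.5 mg/m2; 2400 x 0.75 = 1800 mg/m2; 43/50 - 1 = -14%. Rucaparib, if the 8.1 ladder applies: 500/600 - 1 = -17%.

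| DLT | 7.42: nal-IRI / 5-FU | Section 8: nal-IRI / 5-FU | 7.42 dose relative to Section 8 |
|---|---|---|---|
| Haematologic | 50 / 2400 | 37.5 or 1800, by attribution | +33% for the agent cut |
| Grade 3-4 diarrhoea | 50 / 2400 | 37.5 / 1800 | +33% / +33% |
| Grade 3-4 nausea or vomiting | 50 / 2400 | 43 / 1800 | +16% / +33% |
| Grade 3-4 hand-foot syndrome | 50 / 2400 | 50 / stopped | same / full dose against none |
| Prolonged grade 3 fatigue; grade 3 anorexia | 50 / 2400 | no change required | same; only leucovorin differs |

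The ratios are 50/37.5 - 1 = 2400/1800 - 1 = 33% and 50/43 - 1 = 16%. The fatigue case arises because 7.421 exempts only "CTCAE grade 3 fatigue lasting fewer than 5 days", while footnote a of Table 8.3 requires no change for fatigue. For rucaparib the order reverses: 400/500 - 1 = -20%, so 7.42 is the stricter rule there.

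**Is there a tie-break?**

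- 7.418 requires only that the operations office be told of a DLT.
- The greatest-reduction rule in 8.0 ranks several adverse events in one patient, not two rules for one event.
- 13.1 points to Section 8.0 for unacceptable toxicity but does not mention DLTs.
- 16.2 leaves dose reduction of patients already on a level to the Study Chair(s), without naming either rule.
- 8.21 most plausibly concerns rucaparib: its footnote discusses rucaparib and creatinine, and its companion table 8.22 is for rucaparib. That gives 500 mg BID on the 8.1 ladder and does not say which rule governs chemotherapy.

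**Reach.** 7.12 records DL2-A as already chosen. Under 16.228 that required fewer than 2 DLTs in 6 patients, so at most 1 Phase I patient at DL2-A. For Phase Ib the documents give no rate. Assuming that 5% to 17% (1 in 6) of the 40 planned patients meet DLT criteria gives 40 x 0.05 = 2 to 40/6 = 6.7, about 7, and only if 7.42 applies there.

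**The case against.** The strongest reply is that the conflict depends on what a dose level is. Section 8.1 uses the term for rucaparib alone. On that meaning 7.42 says nothing about chemotherapy, Tables 8.2 and 8.3 govern nal-IRI and 5-FU, and the chemotherapy and leucovorin differences above disappear. This stands as an alternative reading. The 7.11 reading is still the more natural one, because 16.228 uses the same expression for protocol dose levels, but the text does not exclude the other.

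A second reply is that a careful site would satisfy both rules by exceeding neither dose, that the operations office hears of every DLT, and that the Study Chair(s) can intervene. That lowers the practical risk, but none of it is written as a rule of precedence.

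A reader might infer that the protocol obliges sites to resume full-dose chemotherapy with leucovorin, or to restart 5-FU after hand-foot syndrome. The documents do not support that. Continuation is at the investigator's discretion, footnote d of Table 8.3 permits a reduction for most toxicities of grade 2 or higher, and Table 8.3 itself stops 5-FU. A reader might also infer that Section 8 leaves rucaparib untouched after a non-haematologic DLT; 8.21 makes that unlikely.

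On reach, the objection is largely right. DLT is the Phase I endpoint, the DLT form in 18.1 is for Phase I only, and 16.3 plans no DLT analysis for Phase Ib. Against that, 7.4 is headed for both phases.

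**Conclusion.** The point holds conditionally and is minor. If 7.42 refers to the 7.11 levels, it and Section 8 prescribe different chemotherapy for the same DL2-A patient after haematologic, diarrhoea, nausea or vomiting, and hand-foot DLTs. The 7.42 doses are 16% to 33% higher for the agents that Section 8 reduces, and 5-FU continues where Section 8 stops it. If 7.42 refers to rucaparib only, there is no chemotherapy conflict. For fatigue and grade 3 anorexia, nal-IRI and 5-FU agree on either reading.

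Reach is at most one Phase I patient at DL2-A, provided 16.228 was applied. The Phase Ib range of 2 to 7 rests on an assumed DLT rate and on 7.42 applying there. If it does apply, the leucovorin in DL1 would also contradict 7.1, which excludes leucovorin from Phase Ib and II. That contradiction is equally a reason to doubt that 7.42 was meant for Phase Ib.

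It would be wrong to conclude that the dose finding or the efficacy test is compromised. A DLT is counted before the patient resumes, so the 3+3 decision and the MTD stand, and the Phase II endpoint is unaffected.

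**What to change.** Replace the continuation sentence in 7.42 with:

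> Patients who continue after a DLT resume each agent at the lower of the dose at the next lowest dose level and the dose required by Section 8 for that event (including discontinuation); moving to a lower dose level does not raise the dose of any agent or add leucovorin. Later re-escalation follows Section 8.

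Also state whether 7.42 applies in Phase Ib; if it does not, Section 8 alone governs there.

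This works on either meaning of dose level, keeps the re-escalation allowed in 8.21, and leaves footnote a of Table 8.3 intact for chemotherapy. After grade 3-4 diarrhoea at DL2-A, for example, the patient would resume nal-IRI 37.5 and 5-FU 1800 mg/m2 with rucaparib 400 mg BID on the 7.11 meaning, and no leucovorin.

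The cost is a few sentences of text and a slightly larger dose reduction for a few patients. Sample size, visits and data collection do not change.
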